Title: Effectiveness of Orally Dosed Emergency Contraception in Obese Women – UPA

NCT number: NCT02859337

Document Date: March 1, 2016

PROTOCOL FOR CT.GOV

This randomized cross-over study was conducted at Oregon Health & Science University (OHSU) in Portland, OR, USA and Eastern Virginia Medical School (EVMS) Norfolk, VA, USA. The Institutional Review Board (IRB) at OHSU and EVMS approved the study protocol. We recruited healthy women 18-35 years old who with regular menstrual cycles (21-35 days) with a BMI at or greater than 30 kg/m^2 and a weight of 176 lbs or more (80 kg). In addition to this, 12 women with a BMI $<25 \text{ kg/m}^2$ were also recruited as controls. All subjects were required not to be at risk for pregnancy (e.g. abstinent, non-hormonal method of birth control, or non-sperm producing partner). Major exclusion criteria obtained via participant report, review of medical records, and clinical exam included sensitivity or allergy to UPA; treatment for infertility; metabolic disorders including uncontrolled thyroid dysfunction or polycystic ovarian syndrome or clinical evidence of androgen excess; a screening serum progesterone level $<3 \text{ ng/mL}$; impaired liver or renal function; actively seeking or involved in a weight loss program (weight stable) or prior bariatric surgery; pregnancy or seeking pregnancy; breastfeeding; recent (8 weeks) use of hormonal contraception; smoking, vaping, or chronic marijuana use.

After an initial telephone screening, participants completed an in-person screening visit to collect baseline demographic and health information and a serum progesterone level during luteal phase to confirm ovulatory status (progesterone level $\geq 3 \text{ ng/mL}$), an inclusion criterion for participation. All participants completed written informed consent prior to any study procedures. The study was conducted over three menstrual cycles, Cycles 1 and 3 were treatment cycles interspersed by Cycle 2, a washout cycle. For the normal BMI control group, participants only underwent one treatment cycle. We did not have participants undergo a baseline cycle with ultrasound and hormone monitoring. Participants could request to space Cycle 1 and 3 longer than 1 cycle for personal scheduling conflicts or study staff had participants delay an additional cycle, if menses delay occurred in Cycle 2 but if spacing was longer than 3 months, then rescreening would need to take place ($n = 0$). Additionally, our study procedures overlapped with the first

six months of the COVID-19 pandemic resulting in suspended procedures for several months as directed by state and institutional mandates.

Our monitoring procedures were as follows: day 6-8 of treatment cycles 1 and 3, participants came in every other day until a dominant follicle measuring ≥ 15 mm in at least one dimension was visualized.^{7,9,10} These visits consisted of follicular activity monitoring via transvaginal ultrasound and blood sampling for progesterone (P4), estradiol (E2), and luteinizing hormone (LH). After a pregnancy test was performed and the results were negative, the cohort with a BMI at or greater than 30 kg/m^2 and a weight of 176 lbs were randomized to UPA 30 mg or 60 mg for Cycle 1 and then the other dose for Cycle 3. The OHSU research pharmacy maintained the computer-generated randomization scheme and kept treatment assignments in a locked database. Those in the control group, received a single dose of UPA (30 mg) during Cycle 1 only. Following dosing, all subjects were seen daily for blood sampling and ultrasound monitoring until evidence of follicle rupture ($>50\%$ reduction of mean size or complete disappearance of follicle) or for up to 7 days.^{4,7,9,10}

Participants could volunteer for additional study procedures to obtain PK samples. PK parameters were obtained via serum samples through an indwelling catheter. We obtained samples during treatment cycles at the time of dosing at 0.5, 2, 1.5, 2, 3, 4, 24, 48, 72, 96, and 120 hours. PK parameters were generated by noncompartmental methods using WinNonLin (Pharsight, Mountain View, CA). Cmax and time to maximum Cmax are observed values. Area under the curve (AUC) was calculated from Time 0 to 120 hr (AUC₀₋₁₂₀) using the linear trapezoidal rule and then extrapolated to infinity which provide a more accurate calculation of drug clearance (Rowland 1980). Drug half-life (t_{1/2}), oral clearance (CL), and volume of distribution (VD) will be generated using standard pharmacokinetic calculations (t_{1/2} = $0.693/\lambda z$ where λz is the terminal elimination rate constant; CL=dose/AUC_{0-infinity}; VD=CL// λz). Descriptive statistics will be generated for each parameter [mean (standard deviation)], concentration-time curves will be generated for all of the doses and their respective BMI groups. Depending on the

normality of the data, parametric or nonparametric testing will be performed for each parameter between the normal and obese BMI EC 30 mg groups and paired statistics will be utilized to compare obese BMI 30 versus 60 mg UPA groups.

Our primary outcome was the difference in the proportion of subjects with no follicle rupture 5 days post-dosing (yes/no) between dosing groups (30 mg vs 60 mg) in the BMI at or greater than 30 kg/m² cohort. Our main secondary outcome was the timing (day) of follicle rupture between dosing groups in the BMI at or greater than 30 kg/m² cohort. We also calculated these outcomes for our control group and descriptively compared it with the BMI at or greater than 30 kg/m² cohort. If the date of follicle rupture was unclear by ultrasound imaging (e.g. collapse was seen but reduction of size was <50%), we utilized serum hormone levels to adjudicated day of rupture. Two investigators independently reviewed these cycles while being masked to dosing and if a disagreement occurred, a third investigator was engaged.

Hormone assays were performed by The Endocrine Technologies Core (ETC) at the Oregon National Primate Research Center (ONPRC, Beaverton, Oregon (<https://www.ohsu.edu/onprc/endocrine-technologies-core>) performed the hormone, UPA, and Monodemethyl-UPA assays. Serum E2, P4, and LH were analyzed by a Roche Cobas e411 chemiluminescence-based automated immunoassay platform (Roche Diagnostics, Indianapolis, IN). The sensitivities of the E2, P, and LH assays for the Roche e411 are 5 pg/ml, 0.050 ng/ml, and 0.1 mIU/ml, respectively. The intra- and inter-assay variation with the Roche e411 in the ETC is consistently less than 7% for all assays. Quality control sample analyses were repeated prior to each assay run. Serum ulipristal acetate (UPA) and *N*-monodemethylated (NDM)-UPA concentrations were simultaneously determined by ultra-high performance liquid chromatography-heated electrospray ionization-tandem triple quadrupole mass spectrometry (LC-MS/MS) on a Shimadzu Nexera-LCMS-8050 instrument (Shimadzu Scientific, Kyoto, Japan). The lower limit of quantification for both UPA and NDM-UPA was 0.19 ng/ml. Samples with concentrations above 200 ng/ml were re-analyzed after 1:5 dilution in 0 standard. Data processing and analysis were performed using

LabSolutions Software, V5.72 (Shimadzu). Intra-assay coefficient of variation (CV) for UPA ranged from 3.2-14.3% with an inter-assay CV of 6.3% (n=5 assays). Intra-assay CV for NDM-UPA ranged from 2.9-7.4% with an inter-assay CV of 4.5% (n=5 assays). Accuracy was 104.8% for UPA and 106.5% for NDM-UPA. The UPA and NDM-UPA assays were developed and validated largely following FDA guidelines for bioanalytical method validation [FDA Bioanalytical Method Validation Guidance for Industry, 2018] by assessing specificity, stability, precision, accuracy, extraction efficiency (recovery), calibration curve, sensitivity, and reproducibility.

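### If the parametric test is on the raw scale, the normality-dependent rule can give AUC0-infinity and CL different significance verdicts at 30 mg, although they are one quantity

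*Combined protocol and SAP*

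**What the plan says.** All references are to the combined protocol and SAP.

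- **Test rule (pharmacokinetics paragraph).** The choice of test is conditional on distribution: "normality of the data, parametric or nonparametric testing will be performed for each parameter between the normal and obese BMI EC 30 mg groups". No normality test, cut-off, transformation, alpha, lead parameter or multiplicity rule is given.
- **Parameters (same paragraph).** There are seven for UPA. Two are read off directly: "Cmax and time to maximum Cmax are observed values". Two are areas, AUC0-120 and AUC0-infinity, obtained "using the linear trapezoidal rule and then extrapolated to infinity". Three are derived: half-life, "oral clearance (CL), and volume of distribution (VD) will be generated using standard pharmacokinetic calculations".
- **Definition of clearance (same paragraph).** "CL=dose/AUC_{0-infinity".
- **Dose.** The monitoring and dosing paragraph gives controls one 30 mg dose, and the contrast uses the obese women's 30 mg cycle.
- **Group sizes.** The population paragraph says that "12 women with a BMI" below 25 kg/m² "were also recruited as controls". PK sampling was optional: "Participants could volunteer for additional study procedures to obtain PK samples". The number of women with PK data is stated for neither group.
- **Role of PK.** The primary outcome is absence of follicle rupture at 5 days and the main secondary outcome is day of rupture, both compared between doses within the obese cohort. Controls are compared with that cohort only descriptively on these outcomes.

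**The concern.** A rule that picks the test for each parameter from that parameter's own distribution treats AUC0-infinity and CL as separate endpoints. At a common dose they are not. AUC can pass a normality check while its reciprocal fails, or the reverse, so one can go to a t-test and the other to a rank test. Even if both go to a t-test, a raw-scale t-test does not give the same p-value for a variable and for its reciprocal. A report could then say that clearance differed by BMI but exposure did not, or the reverse, from the same measurements.

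This is the only formal test of normal against obese women that the document describes, so any statement that BMI alters UPA exposure would lean on these p-values. A second, separate matter is that every parameter is tested with none carrying the conclusion.

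**Working it through.** The plan states no alpha, power or sample size for this contrast, so there is no figure of its own to reproduce.

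**Inputs from the document:** the test rule, CL = dose/AUC0-infinity, 30 mg in both groups, seven parameters, and at most 12 controls.

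**Assumptions, because the document is silent:** log-normal parameters; a raw-scale t-test as the parametric option and Mann-Whitney as the other; Shapiro-Wilk at 5% in each group, with the t-test used only if both groups pass; two-sided alpha 0.05 per test; and the group sizes and CVs shown below.

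**Step 1, algebra.** CL = 30 mg / AUC0-infinity, so log CL = log 30 − log AUC0-infinity.
- On the log scale the group difference changes sign and the standard error is the same. |t| and p are therefore identical.
- Ranks are reversed, so U becomes n1·n2 − U and the two-sided Mann-Whitney p is the same.
- On the raw scale the mean of 1/AUC is not 1/(mean AUC), so the two t-tests differ.

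In 2,000 simulated trials the largest difference between the AUC0-infinity and CL p-values was about 1e-14 for the log-scale and rank tests, which is rounding.

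**Step 2, how often the verdicts differ under the gated raw-scale rule.** A difference means p<0.05 for one and not for the other.

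| Group sizes, CV | True effect | Verdicts differ |
|---|---|---|
| 12 v 10 or 20, CV 30–70% | none | 1.2–2.7% over repeated runs |
| 12 v 10 or 20, CV 30–70% | exposure ratio 0.7 | 2.9–8.1% over repeated runs |
| 6 v 12, 10 v 10, 12 v 12, 12 v 30; CV 30–80% | none | 0.3–3.1% |
| 12 v 12, CV 30% | CL ratio 1.35 | 7.2% |
| 12 v 12, CV 50% | CL ratio 1.5 | 7.7% |
| 12 v 12, CV 80% | CL ratio 1.8 | 5.4% |

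In the 12 v 10 or 20 setting the two parameters went to different tests in 34–59% of trials. Over the wider set of sizes this was 31–62% of null trials, apart from 8% at 12 v 30 with CV 80%. Among null trials where either was significant, the verdicts differed in 6–47%, typically about a third.

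**Step 3, how large the conflict is.** When the verdicts differed, the larger p-value had a median of about 0.06–0.09 and was below 0.10 in 67–90% of cases.

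**Step 4, power at a ratio of 0.7, CV 50%.**
- 12 v 10: gated rule 37.2% (AUC) and 38.7% (CL); log-scale t-test 38.7%. The change is +1.5 and 0 points.
- 12 v 20: gated rule 52.6% (AUC); log-scale pooled t-test 51.6%; log-scale Welch test 50.5%. The change is −1.0 and −2.1 points.

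**Step 5, multiplicity.** Seven independent tests would give 1 − 0.95^7 = 1 − 0.698 = 30.2%. The parameters are correlated, and simulation gives at least one p<0.05 in 18–22% of null trials (12 v 12: 19.7%, 22.1% and 18.9% at CV 30%, 50% and 80%). Without Tmax it is 15–17%. The document does not say whether parameters of the metabolite NDM-UPA, which is also assayed, are tested; if they are, the figure is 33–37%. Each single test keeps a size of about 4–6%.

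**The case against.** **The scale is unspecified, not wrong.** A parametric test could be a log-scale t-test. If both parameters were tested that way they would agree exactly. This stands, and the disagreement rates are conditional on a raw-scale reading. The text does not exclude that reading, and it plans only raw means and standard deviations as summaries.

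**The conflict is at the margin.** A reader might infer that AUC and CL could show significant effects in conflicting directions, or that the 34–59% routing figure is an error rate. Neither is supported. The conflict is one p-value below 0.05 and the other usually not far above it, and the routing figure describes only the mechanism.

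**The normality check does not produce the one-in-five figure.** It is tempting to link them, but each test holds its size near 5%. The 18–22% comes from reading seven tests unadjusted and would remain under fixed tests.

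**Tmax largely looks after itself.** With discrete Tmax at 12 v 12 (assumed medians 1–2 h, CV 30–50%), the check sent it to the rank test in 75–100% of trials, with size 4–5%. Fixing a rank test mainly writes down what would usually happen.

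**The stakes are low, and the timing is late.** PK is a volunteer add-on with no stated hypothesis. Study conduct is described in the past tense, so a lead parameter named now may be post hoc. Both points stand and limit what can be asked.

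**Conclusion.** The point holds in a limited form. At equal dose the plan tests one quantity twice, under a rule that does not guarantee one answer. On a raw-scale reading, AUC0-infinity and CL receive different significance verdicts in about 1–3% of null trials and 3–8% at a true ratio of 0.7. This rests on log-normal data, 12 v 10–20 women, CV 30–70%, Shapiro-Wilk at 5% and two-sided 0.05, none of which the document states apart from the 12 controls recruited.

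The gain from a fixed test is consistency. The documents and calculations do not support a claim of better power, which moves by about 2–3 points either way. Nor is the trial's main conclusion affected, because it rests on follicle rupture. The 18–22% chance of some false positive among seven parameters is a separate matter of multiplicity.

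**What to change.** For the 30 mg normal v obese contrast:

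- Remove the dependence on normality. Compare log(AUC0-infinity), log(AUC0-120), log(Cmax), log(t1/2) and log(VD) with one fixed t-test, stating whether it is Welch or pooled, and report geometric mean ratios with 95% confidence intervals.
- Compare Tmax with a rank test.
- Report CL as the reciprocal of the AUC0-infinity ratio and interval, with no separate test. This applies only where doses are equal, so it does not carry over to the 30 v 60 mg comparison.
- Label the PK p-values exploratory. AUC0-infinity could be named as the lead exposure measure. If it is named after the data were seen, say so. This last step is optional and more debatable for exploratory PK.

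The cost is a few sentences and a short program change, with no new data or participants. The downside is fewer p-values to quote.

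### The 30 vs 60 mg PK comparison would be better stated as a within-woman 60/30 exposure ratio with a confidence interval, chiefly for Cmax

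*Combined protocol and SAP*

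**What the plan says.** The combined protocol and SAP has no numbered sections. The PK paragraph is its only text on this comparison.

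- Design: obese women "were randomized to UPA 30 mg or 60 mg for Cycle 1 and then the other dose for Cycle 3", so each woman who gives PK samples in both treatment cycles is her own control.
- Sampling: "Participants could volunteer for additional study procedures to obtain PK samples". No PK sample size is given.
- Parameters: "Cmax and time to maximum Cmax are observed values"; "Area under the curve (AUC) was calculated from Time 0 to 120 hr" and was then extrapolated to infinity; clearance is "CL=dose/AUC_{0-infinity"}. Half-life and volume of distribution are also derived.
- Summaries: "Descriptive statistics will be generated for each parameter [mean (standard deviation")], plus concentration-time curves by dose and BMI group.
- Comparison: the choice between parametric and nonparametric tests rests on normality, and for the two doses "paired statistics will be utilized to compare obese BMI 30 versus 60 mg UPA groups".

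No effect measure, interval, scale or named test is given for the two-dose comparison. The primary outcome lies elsewhere: "the difference in the proportion of subjects with no follicle rupture 5 days post-dosing" between the doses.

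**The concern.** The dose is doubled by design, so some rise in Cmax and AUC is expected. The useful PK question is how much exposure the higher dose adds in the same woman, and how precisely that is known. A paired test of undivided Cmax or AUC0-120 against no change shows only that exposure rose. The two means give a rough size for the increase but not its paired uncertainty, because each SD describes spread across women at one dose.

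Total exposure is better served, since CL divides dose by AUC0-infinity. Nothing in the plan does the same for Cmax. At stake is how clearly the PK data can help explain a rupture result in either direction; the rupture analysis itself is untouched.

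**Working it through.** The plan states no PK sample size, power or interval, so there is no figure of its own to reproduce.

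**Inputs.** From the document: doses 30 and 60 mg (dose ratio 2), two periods, CL = dose/AUC0-infinity. Assumed: 6 or 12 pairs, within-woman CV 20/30/40/50%, between-woman log-SD 0.4, log-normal exposure, two-sided 5%.

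**Step 1: what CL covers.** Within a woman, CL60/CL30 = (60/AUC60)/(30/AUC30) = 2/(AUC60/AUC30). A CL ratio of 1 is the same statement as an AUC0-infinity ratio of 2, so a paired comparison of CL tests proportionality of total exposure. It nearly covers AUC0-120 if little area lies beyond 120 h. With mono-exponential decay that share is exp(−0.693×120/t½): 3%, 10% and 18% for assumed half-lives of 24, 36 and 48 h. Cmax is not covered.

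**Step 2: the log-ratio analysis.** The SD of a within-woman log difference is √2 × √ln(1+CV²). At CV 30% this is √2 × 0.2936 = 0.4152. Its standard error is 0.4152/√6 = 0.1695 with 6 pairs and 0.4152/√12 = 0.1198 with 12. Power comes from the noncentral t with n−1 df and noncentrality ln(true ratio/null ratio)/SE:

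- 6 pairs, true ratio 2 against 1: ln 2/0.1695 = 4.09, power 90%.
- 12 pairs, true ratio 1.5 against 1: ln 1.5/0.1198 = 3.38, power 87%.
- 12 pairs, true ratio 1.5 against 2: |ln 0.75|/0.1198 = 2.40, power 59%.

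**Step 3: comparison with a normality-gated paired test** (Shapiro-Wilk on the raw differences, then t or signed-rank), by simulation:

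| Setting | Gated | Log ratio | Gain (points) |
|---|---|---|---|
| Cmax or AUC, against 1; 6 pairs, CV 30%, true ratio 2 | 82% | 90% | 8 |
| Cmax or AUC0-120, against 1; 12 pairs, CV 30%, true ratio 1.5 | 82% | 87% | 5 |
| AUC0-infinity against 2 (gated test on CL); 12 pairs, true ratio 1.5, CV 20/30/40/50% | 86.0/54.5/35.3/24.6% | 89.9/59.3/38.9/27.6% | 3.9/4.8/3.6/3.0 |

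With 12 pairs, CV 30% and a true doubling, every method exceeds 99%.

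**Step 4: the period term.** Neither side of Step 3 adjusts for period. With sequences balanced, adding period leaves the standard error as it is and takes df from n−1 to n−2. At CV 30% the three powers in Step 2 become 86%, 86% and 58%. The cost is about 4 points at 6 pairs and about 1 point at 12.

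**Step 5: precision with 12 pairs.** Median 95% CI factor for the log ratio at CV 20/30/40/50%: ×/÷ 1.19/1.29/1.40/1.51. A paired Fieller interval for the ratio of raw means gives 1.20/1.32/1.45/1.58. At 6 pairs and CV 30% the factors are 1.50 and 1.60.

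**Step 6: what the interval will settle.** An observed ratio of 1.5 with 12 pairs gives 1.5/1.29 to 1.5×1.29, about 1.16–1.94, at CV 30%. At CV 50% it gives about 0.99–2.26. With a true ratio of 1.5 the interval excludes both 1 and 2 in 90/47/15/4% of trials at CV 20/30/40/50%.

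**The case against.** The best defence is that little is missing. Mean (SD) for every parameter at both doses shows the size of the increase, and dividing Cmax by dose is one step. The wording about testing each parameter most naturally extends to the paired comparison, so CL is very likely among the parameters compared. The phrase about paired statistics does not rule out a paired difference with its interval, and a short summary should not be read as a decision to report p-values alone. PK is voluntary, and dose proportionality is not a stated aim. Most of this stands, and it limits the point to the unstated paired interval and to Cmax.

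A reader might infer more, in three ways that the document does not support:

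- That the planned comparison is invalid, or cannot show how large the increase is. It validly shows whether exposure rose, and the two means indicate the size.
- That the plan has no dose-adjusted exposure measure. CL is one.
- That precision improves greatly. That impression comes from rebuilding the ratio from two separate mean (SD) summaries as if unpaired. The plan is paired, and against a paired raw-scale interval the log ratio is only slightly narrower at 12 pairs.

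The defence does not remove the gap itself: no interval for the within-woman increase is stated for any parameter, and no planned parameter stands in for dose-adjusted Cmax.

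**Conclusion.** The omission is real and small: a cheap improvement to consider, not an error. The main gain is a stated effect size with its paired uncertainty, chiefly for Cmax. The gain in power is modest. Before any period term it is about 8 points with 6 pairs and a true doubling, and about 5 points with 12 pairs and a 1.5-fold rise, both at CV 30%. For AUC0-infinity against proportionality it is 3–5 points with 12 pairs.

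All these sizes rest on an assumed PK sample size and assumed CVs. The between-woman SD matters too. With 6 pairs, CV 30% and a true doubling, a plain paired t-test on raw values has power 85/78/66% at between-woman log-SD 0.2/0.4/0.6, against 90% throughout for the log ratio.

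A reader might infer that the trial's dose conclusion is affected. It is not: neither the primary outcome nor the main secondary outcome, the timing of rupture, uses these PK results.

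**What to change.** Replace the unspecified or normality-gated paired comparison of Cmax, AUC0-120 and AUC0-infinity with a log-scale within-woman analysis that includes period, because this is a two-period crossover and a volunteer subset may not be balanced by sequence. Report the 60/30 geometric mean ratio with 95% CI. Read it against 1 (any increase) and against 2 (proportional increase, equivalent to the dose-normalised ratio against 1). Present CL as the same contrast as AUC0-infinity rather than as a separate test. Use a rank method for Tmax.

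The cost is a sentence of analysis text and a few lines of code on samples already planned. The downsides are a little more analysis work, one degree of freedom for period, and intervals that will be wide in a small voluntary subset and will often leave proportionality unsettled.

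### Does the day-of-rupture comparison fail because cycles still unruptured when monitoring ends have no recorded day?

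*Combined protocol and SAP*

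**What the plan says.** The document is a short protocol for ClinicalTrials.gov, written mostly in the past tense. Four places bear on the point.

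- **Outcomes paragraph, secondary outcome.** "Our main secondary outcome was the timing (day) of follicle rupture between dosing groups", in the cohort with BMI of at least 30 kg/m².
- **Outcomes paragraph, primary outcome.** The doses are compared on the proportion with no rupture at 5 days after dosing. Non-rupture is thus an anticipated result with its own endpoint.
- **Monitoring paragraph.** "Following dosing, all subjects were seen daily for blood sampling and ultrasound monitoring until evidence of follicle rupture"; the sentence ends "complete disappearance of follicle) or for up to 7 days". Each woman with BMI of at least 30 kg/m² has two such cycles, one per dose, in randomised order.
- **Rules nearby.** The adjudication rule opens "If the date of follicle rupture was unclear by ultrasound imaging" and concerns ruptures that are hard to date. The sentence "paired statistics will be utilized to compare obese BMI 30 versus 60 mg UPA groups" belongs to the PK paragraph and concerns PK parameters.

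No test is named for any rupture outcome, the primary included. The control group is compared only descriptively.

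**The concern.** A cycle unruptured at the last scan has no rupture day. The text gives it no value, no censoring time and no rank, and neither nearby rule fills the gap. Two analyses are therefore open. One treats unruptured cycles as censored at the last scan. The other compares recorded days only, which keeps ruptured cycles and, within woman, only pairs with a rupture in both.

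The second would be a poor measure of the dose effect on timing. It selects on something that happens after dosing and that the trial expects dose to influence. If 60 mg mainly prevented rupture, the cycles showing its effect would be removed, and the remaining days could look alike, or even earlier, on the higher dose. What is at stake is the main secondary outcome; the primary is unaffected.

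**Working it through.** **Stated figure.** The documents give no sample size for this cohort, no rupture rate and no power, so there is nothing to reproduce. All rates below are assumptions.

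**Step 1: pairs that recorded days can keep.** If shares u1 and u2 are unruptured at day 7 on the two doses, the share of women with a day in both cycles lies between 1 − u1 − u2 (not below 0) and 1 − max(u1, u2).

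| u1 / u2 | Lower | Upper |
|---|---|---|
| 1% / 5% | 94% | 95% |
| 5% / 13% | 82% | 87% |
| 25% / 50% | 25% | 50% |

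**Step 2: how far the two readings can differ.** Take a constant daily rupture hazard h. The share unruptured at day 7 is (1 − h)^7: 0.8^7 = 0.21 for h = 0.20 and 0.9^7 = 0.48 for h = 0.10.

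- Mean day among ruptured cycles: 3.14 v 3.58, difference 0.44.
- Mean day with unruptured cycles held at day 7: 3.95 v 5.22, difference 1.27.
- Share with a day in both cycles, if cycles are independent: 0.79 × 0.52 = 0.41.

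These are different quantities. The first is a mean day given rupture; the second is a restricted mean over all dosed cycles. Part of the gap between them is a change of question, not an error.

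**Step 3: power.** Assume log-normal times with log-SD 0.5, within-woman correlation 0.3, 30 women and days rounded up. Recorded days use a paired t-test on complete pairs. The censored analysis is a discrete-time logistic hazard model with day, dose and period terms and standard errors clustered by woman (simulated type I error 0.045 to 0.059).

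| Median days | Unruptured at day 7 | Pairs kept | Recorded days | Censored hazard | Gain (points) |
|---|---|---|---|---|---|
| 2 v 3 | 1% / 5% | 95% | 87% | 87% | 0 |
| 3 v 4 | 5% / 13% | 84% | 51% | 61% | 10 |
| 5 v 7 | 25% / 50% | 41% | 26% | 65% | 39 |

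If 60 mg only blocks more cycles (10% v 40% blocked, median 4 otherwise; 22% v 48% unruptured in total), the figures are 5% and 51%.

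**Step 4: does the primary outcome see the same effect?** Non-rupture at day 5 under the log-normal model is Φ(ln(median/5)/0.5).

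- 2 v 3: Φ(−1.83) = 3% v Φ(−1.02) = 15%.
- 3 v 4: 15% v Φ(−0.45) = 33%.
- 5 v 7: Φ(0) = 50% v Φ(0.67) = 75%.
- Blocking: 0.10 + 0.90 × 0.33 = 39% v 0.40 + 0.60 × 0.33 = 60%.

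In the two cases where the handling matters most, 5 v 7 and blocking, the primary endpoint differs by 25 and 21 points. A dose effect hidden from recorded days would still bear on the primary.

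**Step 5: what the text permits.** Daily scanning until rupture or a fixed limit yields, for every cycle, a rupture day or a last-scan day. That is the structure of censored time-to-event data. Nothing in the text excludes unruptured cycles or limits the outcome to pairs with two ruptures.

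**The case for a change.** The strongest case for acting is that this is the main secondary outcome, non-rupture is expected, and the handling can change the answer. Under one assumed mixture (25% of cycles rupturing on day 1 or 2 whatever the dose, the rest blocked 10% v 50%), all cycles limited to day 7 give +0.68 day for 60 mg, while recorded days give −0.47 unpaired and −0.43 paired. One sentence and a named method would settle it without new data. Until then a reader cannot tell what a reported difference estimates, or whether the method was chosen after the results were seen.

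Much of this stands. The omission is real, is not a redaction, and a ruptured-only comparison offered as the overall dose effect on timing would be open to criticism. But that criticism applies to an analysis the plan does not prescribe. The absence of a named test is general to this brief document; only the non-rupture rule is particular to timing. A labelled two-part reading (whether rupture occurs, then when among ruptures) is also defensible. The reversal needs an assumed mixture that nothing in the documents supports or rules out. The objection shows that a choice is open, not that a wrong one has been made.

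**Conclusion.** The concern does not call for a change. The outcome is undefined for cycles unruptured at the end of monitoring, but this is missing detail and not a rule that gives a wrong result. Censoring at the last scan fits the text, uses data already collected, and is what an analyst would ordinarily do with daily observations that stop at an event or a limit. A paired rank comparison with non-rupture placed last would serve as well. The primary outcome captures non-rupture at day 5 whichever is used.

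The power difference between recorded days and a censored model is 0, 10 and 39 points in the three log-normal scenarios and 46 points (51% − 5%) in the blocking scenario. All rest on an assumed 30 women, assumed timing and assumed correlation, and the hazard figures hold for clustered standard errors; a random-effect version was not simulated. When nearly all cycles rupture, nothing is gained. The point would matter for a report that dropped unruptured cycles without saying so, which would be a fault of that report.

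### Can a cycle count as unruptured for the primary outcome and still be given a rupture day for the secondary?

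*Combined protocol and SAP*

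**What the plan says.** The combined protocol and SAP has no numbered sections. Three places under its heading Protocol for CT.gov matter.

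- **Monitoring paragraph.** "Following dosing, all subjects were seen daily for blood sampling and ultrasound monitoring until evidence of follicle rupture". The parenthesis that follows requires more than a 50% "reduction of mean size or complete disappearance of follicle) or for up to 7 days". No other ultrasound description of rupture appears.
- **Outcomes paragraph, endpoints.** The primary outcome compares the proportions with "no follicle rupture 5 days post-dosing (yes/no) between dosing groups (30 mg vs 60 mg") in the cohort with BMI of 30 or more. For the secondary: "Our main secondary outcome was the timing (day) of follicle rupture between dosing groups", in the same cohort.
- **Outcomes paragraph, unclear cycles.** Where ultrasound leaves the rupture date in doubt, the plan gives an example and a fallback: "collapse was seen but reduction of size was <50%), we utilized serum hormone levels to adjudicated day of rupture". These cycles are reviewed independently by two investigators masked to dose, and a third is brought in if they disagree.

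The text does not say that an adjudicated day sets the yes/no status for the primary outcome, whether adjudication may conclude that no rupture took place, or which hormone pattern decides.

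**The concern.** A partial collapse of less than 50% does not meet the description in the monitoring paragraph. On that description alone it is not a rupture, and therefore counts as a success for the dose given. The outcomes paragraph uses the same kind of cycle as its example of one needing a rupture day, which presumes that it did rupture. Two analysts could code the primary outcome of one cycle in opposite ways and each cite the plan.

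The use of hormones also looks one-sided. A follicle that shrinks by more than 50%, or vanishes, is accepted as ruptured even if LH and progesterone show no ovulation, although both are drawn at each visit. The study relies on progesterone elsewhere: at screening it takes a "serum progesterone level during luteal phase to confirm ovulatory status". If follicles that regressed without rupturing were counted as ruptures, a dose that suppresses ovulation more strongly could be penalised.

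At stake is a binary primary outcome in a crossover that may be small, where a few recoded cycles could matter.

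**Working it through.** The plan has no figure to reproduce: it gives no sample size, alpha, test or expected rupture rate for the primary comparison. The check is therefore a side-by-side reading, followed by the size of the effect.

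**1. Each type of cycle under the two rules**

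| Cycle | Primary (day 5) | Secondary (day) | Settled by the text? |
|---|---|---|---|
| Fall of more than 50%, or follicle gone, by day 5 | rupture | that day | yes |
| Same, on day 6 or 7 | no rupture | day 6 or 7 | yes, by design: follow-up runs to day 7, the primary stops at day 5 |
| Partial collapse, adjudicated day 5 or earlier | no rupture if the monitoring wording governs; rupture if the adjudicated day governs | adjudicated day | not in words |
| Fall of exactly 50% | meets neither the rule nor the example | not stated | open, but the trigger is any unclear date and the partial collapse is only an example |

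Only the third row gives two answers. The pattern of no rupture on the primary with a day on the secondary is not in itself an error, as the second row shows.

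**2. Which reading the text favours**

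- The 50% wording is attached to when daily visits end. It is not placed in the sentence that defines the primary outcome, and nothing limits that outcome to ultrasound.
- The fallback comes directly after both outcomes are named and is not reserved for the secondary.
- The trigger is an unclear date, with some collapse seen. A follicle may collapse partly at one visit and pass 50% at a later one. Then rupture is not in doubt, only its day, and the day decides whether it falls within five days.
- The primary follows from the day: an adjudicated day of 5 or earlier is a rupture by day 5. One variable serves both outcomes.

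**3. Are hormones available where they are needed?**

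A partial collapse does not meet the stopping rule, so daily sampling continues, to day 7 if need be. Assessors can therefore see whether progesterone rises afterwards. A clear rupture ends the visits, so a later rise would often go unsampled. Hormones are thus used where the data can support a judgement.

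**4. Size**

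Let k30 and k60 be the numbers of cycles in the third row at each dose, and N the women per dose period. Moving from the adjudicated to the literal reading raises each success proportion by k/N, so

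change in the 60 mg minus 30 mg difference = (k60 − k30)/N.

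Equal numbers at the two doses leave the difference unchanged. For an imbalance of one cycle, with N assumed:

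- N = 20: 1/20 = 5.0 points
- N = 30: 1/30 = 3.3 points
- N = 50: 1/50 = 2.0 points
- N = 60: 1/60 = 1.7 points

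In the 12 controls, one cycle is 1/12 = 8.3 points, but that comparison is descriptive only.

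If an exact McNemar test were used (the plan names none for this outcome), the two-sided p-values for discordant pairs are:

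- 5 v 0: 2/32 = 0.063; 6 v 0: 2/64 = 0.031
- 7 v 1: 2(1 + 8)/256 = 18/256 = 0.070; 8 v 1: 2(1 + 9)/512 = 20/512 = 0.039

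One cycle can cross 0.05 in these cases, but the counts were picked at that edge. The same holds for any single recoded cycle in any small paired study, and the documents do not say how often unclear cycles arise.

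**The case for a change.** The strongest case for a change is that a primary endpoint should not rest on an inferred rule. The only written description of rupture excludes the very cycle that the plan then dates. Masking keeps knowledge of dose out of the judgement, but it does not say what is being judged, by what criterion, or whether the answer feeds the primary. A sentence or two would close the gap at almost no cost, and an ultrasound-only sensitivity analysis would show whether it mattered.

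Part of this stands: the link is unwritten and the hormone criterion is missing. It shows an omission, though, and not two rules that contradict each other. Because the assessors do not know the dose, whatever working rule they adopt cannot be applied differently by dose on purpose.

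The case for checking hormones in clear ruptures is weaker. It is fair that no such check is described. But the outcome is rupture of the follicle, not hormonally confirmed ovulation, so requiring an LH surge or progesterone rise would alter the endpoint. The screening progesterone is an entry criterion and says nothing about how the endpoint is classified. The documents do not indicate how often a follicle of at least 15 mm would shrink by more than half within seven days without rupturing, and give no suppression rates by dose. A bias against 60 mg is therefore a presumption. The text also describes a study already conducted, so a new two-way review would be a post hoc redefinition and not just a clarification.

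**Conclusion.** No change is needed. The text leaves unsaid that an adjudicated rupture on or before day 5 counts as a rupture for the primary outcome, and it gives no hormone criterion. The placement of the fallback, and the fact that the yes/no status follows from the day, point to a single rupture day for both outcomes. Analysts and dose-masked assessors would fill the gap that way. A rupture on day 6 or 7 that counts as no rupture for the primary is intended.

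The possible effect is confined to the imbalance between doses in partial-collapse cycles: 5.0 to 1.7 points per cycle of imbalance, on the assumption of 20 to 60 women. The number of such cycles cannot be known from the documents. Leaving clear ultrasound ruptures without a hormone check is a fair trade-off, given the endpoint chosen and the end of sampling at rupture.

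The conclusion rests on reading the 50% wording as a monitoring endpoint with adjudication as its fallback. A statement that the primary outcome is ultrasound-only would overturn it, and the documents contain none.
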